9.4.2. Primary Endpoint

The primary efficacy analysis will be based on the ITT analysis set restricted to participants with confirmed critical COVID-19 disease and the primary efficacy endpoint is the ‘time to improvement of at least 2 categories relative to Baseline on a 6-point ordinal clinical recovery scale’. The improvement should be sustained until Day 28 (or discharge/discontinuation). Time to clinical improvement will be assessed during the 28-day period after study drug administration, with failure to reach clinical improvement or death before Day 28 considered as right-censored at Day 28.

This primary parameter will be analyzed by a stratified log-rank test (using the stratification factors). Kaplan-Meier curves, overall and by stratum will be used to graphically present the primary parameter. The sensitivity analyses will be defined in the statistical analysis plan.

First, the primary endpoint will be tested for superiority of sirukumab over placebo at the 2-sided 5% significance level. If superiority is shown on the primary endpoint, then the key secondary endpoints will be tested at the 1-sided 5% significance level.

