9.4.5. Exploratory Endpoint(s)

Time to viral negativity will be analyzed analogously to that of the primary efficacy parameter.

SARS-CoV-2 viral load in NP swabs and in endotracheal, blood, and stool samples will be measured by a qRT-PCR assay. These data will be analyzed graphically and descriptively as described in the statistical analysis plan.

Other exploratory parameters might be added in the SAP.

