5.2.3 Analysis Methods

All participants for which the trial is still ongoing at Day 28 and without sustained clinical improvement by Day 28 will be censored on Day 28. Participants that discontinue the study before day 28 will be censored at the last assessment of the CRS, unless they had an event of sustained clinical improvement prior to discontinuation. Participants that died at day 28 or earlier will be censored at day 28, irrespective of whether a clinical improvement occurred prior to death.

The primary hypothesis of this study is that Sirukumab in combination with SOC results in a statistically significant shorter time to sustained improvement (defined as an improvement of at least 2 categories relative to baseline on the 6-point ordinal CRS) versus placebo in combination with SOC, in participants with confirmed critical COVID-19.

The primary hypothesis will be evaluated based on the Logrank test, stratified for the stratification factors (age [<65 and ≥ 65 years] and use of IMV [yes/no]). This test will be performed 2-sided at a 5% significance level. The actual values of the stratification factors will be used, not as randomized.

The hazard ratio of sustained clinical improvement for experimental treatment versus placebo, from baseline until day 28 will be considered as the population-level summary measure of the treatment effect for the primary estimand. The hazard ratio will be estimated in a Cox proportional hazards model stratified for the stratification factors and with treatment as a single covariate. A value larger than 1 indicates the chance of improvement is larger in the experimental treatment group. The 95% Wald confidence interval will be added.

The Log-rank test might generate a different p-value compared to that of the Wald test of the hazard ratio. The Logrank test will be used for formal inference (and not the Wald p-value or CI from the hazard ratio).

Cumulative proportion of patients with clinical improvement, by treatment, will be provided using the complement of the Kaplan Meier curve. The analyses will be completed with the median time to clinical improvement (if reached) and the proportion of participants who had their clinical improvement on day 7, 14, 21 and 28; all per Kaplan Meier method. The complementary log-log transform method is used to calculate the 95% confidence intervals.

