6.5 Analysis of Undetectability of Viral Load

For the analysis of undetectability of viral load all subjects with at least a post-baseline measurement of viral load by Nasopharynx assay will be considered.

For the primary analysis, all measurements of viral load up to Day 31 of the study (i.e. protocol window: Day 28+3 days) by the NP assay from central lab (central lab) will be used. Plots for individual participants will be generated using data up to Week 16.

Time (Days) to undetectability of virus load will be evaluated using the **First confirmed undetectability (CU)** approach as described below.

First confirmed undetectability (CU)

A participant is said to have (CU) of viral load if (1) participant has two consecutive undetectable viral loads, or (2) if the last viral load in the database is undetectable.

If there is at least one incidence of the CU then the date of the first undetectability among all CUs will be used to find the days from the study dose date to first CU of viral load. If there is no CU until study Day 31 then participant will be censored at date of last viral load assessment until study Day 31.

Following rules will be applied to derive the flags for event (of first CU) or censoring, and to derive the Days to event or censoring.

[For clarity, in the examples below of different cases a detectable viral load is denoted by 'D', and undetectable by 'U', and 'x' will represent any type of load (undetectable or detectable)].

(1) Case when a participant has only 1 viral load measurement in database (therefore it is also the last viral load measurement):

- a. If the viral load is undetectable then censor flag = No (same as Event = Yes) [example: U => censor flag = No],

Days to event = date of last viral load measurement – dose date + 1.

- b. Otherwise if the viral load is detectable then censor flag = Yes (same as Event = No),
[example: D => censor flag = Yes].

Days to censoring = date of last viral load assessment – dose date + 1.

(2) Case when a participant has more than 1 viral load measurements in the database:

- a. if there are no cases of 'CU cases based on 2 consecutive viral loads' then
 - i. if last viral load in the database is undetectable then

censor flag = No (same as Event = Yes),
 [example: U₁DDU₂DU₃DU₄ => censor flag = No],

ii.if last viral load in the database is detectable then
 censor flag = Yes (same as Event = No),
 [example: U₁DDU₂DU₃D => censor flag = Yes],

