In both these cases a(i) and a(ii), the 'Days to event/censoring' will be based on the date of last viral load measurement until study Day 31 in the database.

b. If there are one or more CU cases based on 2 consecutive viral loads then
 censor flag = No (same as Event = Yes),
 and 'Days to event/censoring' will be derived using date of first viral load among the viral loads resulting in CU cases.

[examples: DU₁DU₂U₃D or U₁DU₂U₃U₄DU₅U₆ => censor flag = No,
 and in both cases 'Days to event/censoring' = Days to U₂).]

Summary and Kaplan-Meier Analysis of Time to Undetectability of Viral Load:

The analysis of time-to first CU of viral load is planned by the Kaplan-Meier (KM) analysis. Days to first CU of viral load will also be summarized using the quartiles (and their confidence intervals). The analysis will be performed for ITT and Primary analysis sets. (Note: As per the inclusion criteria of the protocol all participants in the study are detectable for viral load at baseline. Therefore, all participants in the ITT and Primary analysis sets will be included for these analyses, respectively).

For the primary analysis, non-missing planned and unscheduled measurements will be used to generate the summary tables showing n and percentage (cumulative) of participants with CU by Day 3, 7, 10, 14, 21, 28/31. For the final analysis, table will also include Week 16.

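### SAP 6.5 has no rule for death in time to undetectable virus and plans no arm comparison: an unexplained departure from protocol 9.4.5 that makes its Kaplan-Meier curve and quartiles overstate clearance

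*SAP*

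**What the plan says.** - **Protocol 9.4.5:** "Time to viral negativity will be analyzed analogously to that of the primary efficacy parameter".
- **Primary parameter, protocol 9.4.2:** a log-rank test stratified by the randomization factors, "with failure to reach clinical improvement or death before Day 28 considered as right-censored at Day 28".
- **Primary parameter, SAP 5.2.3:** the same test, with a stricter death rule: "Participants that died at day 28 or earlier will be censored at day 28, irrespective of whether a clinical improvement occurred prior to death".
- **Viral endpoint, SAP 6.5, event:** confirmed undetectability (CU) is two consecutive undetectable loads, or it is met "if the last viral load in the database is undetectable".
- **Viral endpoint, SAP 6.5, censoring:** with no CU by Day 31, the "participant will be censored at date of last viral load assessment until study Day 31". Death is not mentioned.
- **Viral endpoint, SAP 6.5, output:** "The analysis of time-to first CU of viral load is planned by the Kaplan-Meier (KM) analysis", with quartiles and their confidence intervals, and also "summary tables showing n and percentage (cumulative) of participants with CU by Day 3, 7, 10, 14, 21, 28/31". No test of treatment is named.
- **Status:** SAP 6.1 calls the viral load analysis exploratory.

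**The concern.** The protocol ties this endpoint to the primary one. The SAP carries over neither of the two features that define the primary analysis: the stratified comparison and the holding of deaths in the risk set. It does not say that it departs, or why. Elsewhere the SAP does write a death rule for each endpoint where one is needed. In 5.4.1, for example, deaths are censored at Day 28 for time to ICU discharge.

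The statistical consequence is the usual competing-risk one. A participant who dies still positive leaves the risk set at the last swab, and Kaplan-Meier then credits that person with the later clearance seen in those still being swabbed. The plan assumes 40% mortality on control and 20% on sirukumab, so the error is neither small nor expected to be equal in the arms. Viral clearance is a natural question for an immunosuppressant given during active infection, and these curves are where a reader would look for it.

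**Working it through.** **The plan's own figures.** The documents give none for the viral endpoint. The nearest are for the primary endpoint with deaths held to Day 28, and they reproduce:
- Control improvement at Day 28 is (1 − 0.40) × 0.50 = 30%, as stated.
- Sirukumab is 0.80 × Φ(ln(28/16.8)/0.9) = 0.80 × 0.715 = 57.2%, against a stated target of 55%.
- Simulated log-rank power with 74:37 participants is 81.4%, against at least 80% stated.

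**Inputs for the viral endpoint**
- Swab days 3, 7, 10, 14, 21 and 28 (SAP 6.4).
- Day 28 mortality m of 20% or 40% (SAP 1.4).
- Assumed: a proportion p would clear by Day 28 if nobody died, at a constant rate that is equal in the arms and unrelated to death, and cleared participants stay undetectable. Then the proportion still detectable at day t is G(t) = (1 − p)^(t/28).
- Assumed death timing, two versions for the proportion alive S(t). Uniform over Days 3 to 28: S(t) = 1 − m(t − 3)/25. Constant hazard from dosing: S(t) = (1 − m)^(t/28).

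**Formulas**
- Last-swab censoring (SAP 6.5): anyone who dies uncleared is removed before the next swab, so the curve reaches 1 − G(28) = p at any mortality.
- Proportion who actually clear: Σ S(t_k) × [G(t_(k−1)) − G(t_k)] over the six swabs.

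**Worked case:** p = 70%, m = 40%, uniform deaths.
- The falls in G between swabs are 0.1210, 0.1389, 0.0896, 0.1028, 0.1424 and 0.1054.
- S at the swabs is 1, 0.936, 0.888, 0.824, 0.712 and 0.600.
- The sum of products is 0.1210 + 0.1300 + 0.0796 + 0.0847 + 0.1014 + 0.0632 = 0.580. The curve shows 70%, so the overstatement is 12.0 points.

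**All cases at Day 28 (actually cleared; overstatement in points)**

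| Curve shows | Deaths | 20% mortality | 40% mortality |
|---|---|---|---|
| 50% | uniform | 45.2%; 4.8 | 40.5%; 9.5 |
| 50% | constant hazard | 44.5%; 5.5 | 38.5%; 11.5 |
| 70% | uniform | 64.0%; 6.0 | 58.0%; 12.0 |
| 70% | constant hazard | 62.9%; 7.1 | 55.1%; 14.9 |
| 85% | uniform | 78.8%; 6.2 | 72.5%; 12.5 |
| 85% | constant hazard | 77.3%; 7.7 | 68.8%; 16.2 |

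Simulations of the same set-ups (uniform deaths at all three clearance rates, constant hazard at 50% and 70%) agree to within about 0.1 point. Under constant hazard, about 5% (40% mortality) and 2% (20% mortality) die before the first swab. They are counted here as not cleared, but drop out of the Kaplan-Meier analysis.

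**Quartiles.** Take p = 85% with uniform deaths. The curve at Day 21 is 1 − 0.15^0.75 = 75.9%, so the reported 75th percentile is Day 21 in both arms. The proportion actually cleared is 71.5% at Day 21 and 78.8% at Day 28 with 20% mortality, so the percentile is Day 28. With 40% mortality it is 72.5% at Day 28, so the percentile is not reached.

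**Direction by arm.** With equal clearance, the error at 40% mortality is about twice that at 20%. The order is unchanged if those who die clear at half the rate, or not at all. It reverses when clearance is much faster in the arm with fewer deaths: with 20% clearance on control and 70% on sirukumab (constant hazard), the overstatement is 4.9 and 7.1 points.

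**The exact primary rule.** If every death by Day 28 is a non-event, the proportion is (1 − m)p. At p = 70% that is 56% and 42%, which is 14 and 28 points below the curve.

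**The case against.** **The SAP may fill in detail.** Protocol 9.4.5 states no death rule; the Day 28 rule follows only by reading it with 9.4.2. Protocol 9.4.7 describes virology time-to-event output as numbers included and censored, median and quartiles, with no test, and SAP 6.5 fits that. Death enters the primary endpoint because it is the worst category of the clinical scale, and viral load has no such category. This stands as far as it goes: a reader might infer that the protocol spells out the death rule, and it does not. It does not explain why the comparison and the death handling are absent without comment.

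**Last-swab censoring answers a legitimate question.** If the drug leaves clearance unchanged, equal curves are the correct cause-specific answer, and holding deaths at risk lets a survival difference appear as a viral one. In 4,000 simulated trials (74:37, equal clearance of 50/70/85%, uniform deaths, 20% against 40% mortality, unstratified log-rank at 5%), rejection rates were 4.8/4.6/5.7% with last-swab censoring and 6.7/7.6/8.6% with uncleared deaths held at risk. Under the exact primary rule they were 17/28/38%. This stands, and is why the present analysis should be kept beside the new one. It does not rescue the curve as a statement of how many participants clear.

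**Not every output is affected.** A reader might infer that SAP 6.5 reports the complement of Kaplan-Meier. Those words are in 5.2.3 and 5.4.2, not in 6.5. Its table of cumulative n and percentage is not said to come from Kaplan-Meier; as a crude percentage it would be close to the proportion who clear. The quartiles, however, are read from the affected curve.

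**Conclusion.** The point holds as an unexplained departure from protocol 9.4.5, with a predictable bias in the Kaplan-Meier curve and quartiles. At the plan's own mortality rates, and with assumed clearance of 50% to 85% that is equal in the arms, the curve overstates clearance by 4.8 to 7.7 points at 20% mortality and 9.5 to 16.2 points at 40%. The ranges rest on the assumed clearance and death timing. The mortality rates are planning values for critical participants; SAP 6.5 also analyses the ITT set, which includes about 100 severe participants.

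A reader might go further and infer that clearance is always overstated most in the arm with more deaths. The documents do not support that: it needs clearance that is similar in the arms, or faster in the arm with more deaths.

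The consequence is limited. The endpoint is exploratory, lies outside the testing hierarchy and has no bearing on the stated power.

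**What to change.** In SAP 6.5:
1. For the curves and quartiles, keep participants who die without prior confirmed undetectability at risk to the end of the Day 28/31 window. Equivalently, report cumulative incidence with death as a competing event.
2. State whether clearance before death counts as an event. Item 1 assumes that it does; the exact rule in 5.2.3 would make it a non-event, so the choice needs to be written down.
3. Add the log-rank test stratified by age and invasive mechanical ventilation that protocol 9.4.5 implies.
4. Keep the last-swab-censored, cause-specific analysis as a supportive display, because the comparison with deaths at risk also reflects mortality.
5. Keep last-swab censoring for living participants who stop being sampled.
6. Say whether the cumulative n (%) table is a crude percentage.

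The cost is a few lines in the SAP and one extra exploratory output. Death dates are already collected.

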 - General safety chemistry: total protein, albumin, aspartate aminotransferase (AST), alanine aminotransferase (ALT), alkaline phosphatase (ALP), total bilirubin, glucose, sodium, potassium, calcium, phosphate, magnesium, chloride, bicarbonate, creatinine, blood urea nitrogen (BUN), creatine phosphokinase (CPK), lactate dehydrogenase (LDH), lactate, and troponin. If ALT or AST >3x ULN or 3x the entry level (if entry levels were >ULN), also provide conjugated bilirubin (direct), unconjugated bilirubin (indirect).
- m. Culture results (bacterial, fungal, or viral) including site of infection and specimen source (bronchoalveolar lavage [BAL], tracheal aspirate, sputum, blood, urine, etc.), performed as part of patients' workup for new infections, should be reported. Analyses will be performed by the local laboratory.
- n. For participants discharged or who discontinued the study prior to Day 28 and did not withdraw consent, phone calls will be conducted on Day 28 and during the post Day 28 Follow-up Phase to record concomitant medication, the vital status, the occurrence of AEs, self-reported oxygen need, self-reported pregnancy status and the history of readmission since last contact.
- o. Whenever possible, vital status will be recorded if the patient is alive. If the participant is deceased, date and cause of mortality should be recorded in the eCRF. Death should be documented as SAE.
- p. NP swabs will be used to collect secretions from participants to explore quantification of viral load of SARS-CoV-2. For each participant, NP sampling should be done at approximately the same time (± 4 hours) on each sampling day and from the same nostril.
- q. If an NP sample for detection of SARS-CoV-2 (local SOC) will be collected on the same day as the NP sample for quantification of SARS-CoV-2 (central lab), only one NP sample should be collected. The sample should be aliquoted and the remaining aliquots of the NP samples should be stored and sent to the central lab for quantification of SARS-CoV-2.
- r. SARS-CoV-2 positivity should be documented based on local testing on any specimen, by RT-PCR, any time before randomization. This might require a local test using an NP swab obtained at screening.
- s. After randomization, SARS-CoV-2 positivity will be confirmed in a central lab by quantitative RT-PCR. The baseline sample needs to be collected predose, as close as possible to dosing.

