5. STUDY POPULATION

Screening assessments start after signing of the ICF and can continue on the next calendar day, if needed. All screening and baseline assessments may also take place on the same day. Results from the blood test, pregnancy test, ECG, and pulmonary imaging, completed as SOC, taken up to 2 days prior to screening will be accepted as screening assessments. SARS-CoV-2 positivity, as determined locally by real time-PCR, in any specimen at any time prior to randomization is acceptable and this should not be repeated for inclusion in the study. If all eligibility criteria are met at screening then randomization may occur on that same day.

The inclusion and exclusion criteria for enrolling participants in this study are described below. If there is a question about these criteria, the investigator must consult with the appropriate sponsor representative and resolve any issues before enrolling a participant in the study. Waivers are not allowed.

For a discussion of the statistical considerations of participant selection, refer to Section [9.2](#), Sample Size Determination.

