5.1. Inclusion Criteria

Each potential participant must satisfy all of the following criteria to be enrolled in the study:

1. Male or female ≥ 18 and < 85 years of age.
2. Hospitalized.
3. Criterion modified by Amendment 4
 - 3.1 Has laboratory-confirmed SARS-CoV-2 infection as determined by real time-PCR at any time before randomization.
4. Criterion modified per Amendment 3
 - 4.1 Evidence of infiltrates by chest X-ray, chest CT, lung ultrasound, or chest auscultation (rales, crackles).
5. Criterion modified per Amendment 2
 - 5.1 Criterion modified per Amendment 3
 - 5.2 Criterion modified per Amendment 5
 - 5.3 Critical COVID-19 disease, defined as:

Critical disease: Requires supplemental oxygen delivered by nonrebreather mask or high-flow nasal cannula OR use of non-invasive or invasive ventilation OR requiring treatment in an ICU.

AND,

corresponding to category 4 on the 6-point ordinal recovery scale (see Section 8.1.1), ie,

Requires one of the above modalities to sustain a $\text{SpO}_2 > 93\%$, with an FiO_2 of 50%^a or higher. Note, the use of other devices may fit with category 4 if the FiO_2 is 50%^a or higher.

OR, corresponding to category 5 on the 6-point ordinal recovery scale, ie,

$\text{PaO}_2/\text{FiO}_2$ ratio < 300 mmHg while on invasive mechanical ventilation or veno-venous ECMO for less than 48 hours prior to screening.

Note: as of protocol amendment 5, patients with confirmed severe COVID-19 disease are no longer eligible in the study. Severe COVID-19 is defined as requiring supplemental oxygen administration by nasal cannula, simple face mask, or other similar oxygen delivery device (ie, above pre-COVID baseline oxygen requirement,

^a The conversion between the oxygen flow expressed in L/min to the corresponding FiO_2 value in % is the following:

L/min	1	2	3	4	5	6	7	8	9	10
FiO_2 %	24	28	32	36	40	44	48	52	56	60

if any, by the participant) at a FiO_2 less than 50%^a. This corresponds to category 3 on the 6-point ordinal scale (see Section 8.1.1).

6. Criterion modified per Amendment 1

6.1 Informed consent must be obtained from the participant (or their legally acceptable representative must sign based on local regulations) indicating that he or she understands the purpose of, and procedures required for, the study and is willing to participate in the study.

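### SAP 6.5 assumes that everyone has detectable virus at baseline, which eligibility does not ensure, so participants undetectable at baseline and at the early visits are counted as clearing virus

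*SAP*

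**What the plan says.** SAP 6.5 analyses time from dosing to first confirmed undetectability (CU) of viral load. CU is reached with two consecutive undetectable results, or "if the last viral load in the database is undetectable". With two consecutive results the event is dated to the first of them. For the primary analysis, measurements up to Day 31 "by the NP assay from central lab (central lab) will be used". The planned output is a Kaplan-Meier analysis, quartiles with confidence intervals, and a table of cumulative CU by Day 3, 7, 10, 14, 21 and 28/31.

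On who is analysed, a note in SAP 6.5 says that under the protocol's inclusion criteria "all participants in the study are detectable for viral load at baseline". It concludes that "all participants in the ITT and Primary analysis sets will be included for these analyses". The opening sentence of the same section says something different: "all subjects with at least a post-baseline measurement of viral load by Nasopharynx assay will be considered".

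The criterion behind the note is Protocol 5.1, criterion 3.1: "Has laboratory-confirmed SARS-CoV-2 infection as determined by real time-PCR at any time before randomization". Protocol Section 5 adds that "SARS-CoV-2 positivity, as determined locally by real time-PCR, in any specimen at any time prior to randomization is acceptable" and that the test need not be repeated for inclusion. Footnote s of the Schedule of Activities states: "After randomization, SARS-CoV-2 positivity will be confirmed in a central lab by quantitative RT-PCR".

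**The concern.** Time to undetectable virus has no meaning for someone who has none detectable at the start. If the eligibility test and the endpoint test can disagree on Day 1, some participants enter with nothing to clear on the endpoint assay. Under the CU rule, those who stay undetectable become very early events in either arm. The Kaplan-Meier quartiles then come out too short, and the early rows of the CU table mix true clearance with absence of virus at entry. Any comparison of arms is pulled toward no difference.

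SAP 6.5 itself names no test. The comparison comes from Protocol 9.4.5, which has time to viral negativity handled like the primary parameter, and Protocol 9.4.2 analyses that by stratified log-rank test. The change-from-baseline summaries in SAP 6.4 are affected by the same participants.

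**Working it through.** **1. The eligibility test against the endpoint test.**

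| | Eligibility (Protocol 5, 5.1) | Endpoint (SAP 6.2, 6.5) |
|---|---|---|
| Laboratory | Local | Central |
| Specimen | Any | Nasopharyngeal |
| Timing | Any time before randomization | Last pre-dose sample, or the first within 60 minutes after dosing if there is none |
| Gate to entry? | Yes | No; confirmed after randomization |

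Nothing in the left column forces a detectable result in the right one. The premise of the note does not follow from the criterion it cites.

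**2. What the CU rule does with an undetectable baseline.** Write U for undetectable and D for detectable. The rule was coded and returned the SAP's own result for all six of its example sequences. It requires no D before the first U. Applied to the sampling days (1, 3, 7, 10, 14, 21, 28):

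- U at every visit: event on Day 1 if the baseline sample belongs to the sequence, on Day 3 if only later samples count. SAP 6.5 does not say which.
- U at baseline, D on Day 3, U from Day 7: event on Day 7, not an early event.
- The SAP's example U D D U D U D is censored. Its example U D D U D U D U is an event at the last result.

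**3. Change from baseline.** SAP 6.3 imputes an undetectable result as 1 copy/mL, so log10 = 0. The lowest detectable nasopharyngeal value is LLOQ/2 = 1018/2 = 509 copies/mL, and log10(509) = 2.71. From an undetectable baseline the change is therefore either 0 or at least +2.71; it cannot be negative.

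**4. Size.** The plan gives no figure for this endpoint to reproduce. Everything here except the sample size and sampling days is assumed: share undetectable at baseline p = 0% to 30%, all of whom stay undetectable; exponential clearance in the others with a control median of 14 days; true clearance hazard ratio (HR) 1.5; no deaths, dropout or false negatives.

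*Events by Day 3.* The control rate is ln 2/14 = 0.0495 per day.
- Control: 1 − exp(−0.0495 × 3) = 13.8%.
- Sirukumab: 1 − exp(−0.0495 × 1.5 × 3) = 20.0%.
- Pooled 2:1: (2 × 20.0 + 13.8)/3 = 17.9%.
- With share p: p + (1 − p) × 17.9% = 26%, 34% and 43% at 10%, 20% and 30%.

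*Control median.* Solve p + (1 − p)(1 − exp(−0.0495t)) = 0.5, which gives t = ln[(1 − p)/0.5]/0.0495. The 14 days become 11.9, 9.5 and 6.8 days. Read off the sampling days, the median is Day 14, 14, 10 and 7 for p = 0%, 10%, 20% and 30%.

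*Between-arm comparison.* Simulation with 74 versus 37 participants (Protocol 9.2), an unstratified two-sided 5% log-rank test and 1,500 replicates. The HR is taken as exp of the mean of (O − E)/V, an approximation that gives 1.56 at p = 0 for a true 1.5. Read the fall, not the level.

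| p | HR, baseline sample counted | HR, post-baseline samples only | HR, restricted to detectable baseline | Power, baseline counted vs restricted |
|---|---|---|---|---|
| 0% | 1.56 | 1.56 | 1.56 | 43% vs 43% |
| 10% | 1.47 | 1.49 | 1.56 | 35% vs 41% |
| 20% | 1.41 | 1.45 | 1.57 | 30% vs 37% |
| 30% | 1.34 | 1.39 | 1.57 | 23% vs 34% |

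With about 211 participants (severe and critical) the HR with the baseline sample counted goes from 1.55 to 1.46, 1.40 and 1.36. The restricted analysis keeps the HR and loses some power only because it is smaller.

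**The case against.** The strongest reply accepts that the note is inaccurate and disputes how much follows from it.

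- **The two-result requirement protects against isolated negatives.** This stands. A reader might infer that everyone undetectable at baseline becomes an early event; the SAP's own sequences starting with U and followed by D show otherwise. The harm is confined to participants who stay undetectable at the early visits or who have very few samples. The figures above assume that all of them stay undetectable, so they are upper values for a given share.
- **SAP 6.5 plans no hazard ratio.** This stands too. A reader might infer that a planned estimate is biased. In SAP 6.5 the harm falls on the curves, the quartiles and the CU table; the HR figures illustrate a comparison that rests on Protocol 9.4.5 alone.
- **The affected share may be small.** Some participants qualify on a nasopharyngeal swab taken at screening, and one swab is aliquoted for both laboratories when the two samples fall on the same day (Schedule of Activities, footnotes q and r). This may limit the share, but it does not support a statement about all participants.
- **SAP 6.4 already shows absolute loads and individual profiles.** Undetectable baselines would be visible there. That helps an attentive reader but does not correct the time-to-event output.
- **The endpoint is exploratory.** True, and it limits how much weight the point can carry.

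**Conclusion.** The statement in SAP 6.5 is wrong as written: the inclusion criteria do not make every participant detectable on the central nasopharyngeal assay at baseline. Participants who are undetectable at baseline and remain so at the early visits are recorded as clearing virus on Day 1 or Day 3 regardless of arm.

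The direction is certain if there are any such participants; the size is not known. Under assumed shares of 10% to 30%, an assumed true HR of 1.5 and assumed clearance rates, the HR is attenuated to roughly 1.5 to 1.3, and the pooled share with an event by Day 3 rises from 18% to between 26% and 43%. At a share of 0% there is no effect. With no treatment effect, these events occur alike in both arms in expectation, so the flaw dilutes a difference and does not create one.

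It would be too strong to conclude that the trial's efficacy findings are compromised. SAP 6.1 labels viral load exploratory, and no primary or key secondary conclusion depends on it. The correction is still worth making, because the endpoint is listed in the objectives and its analysis set rests on a misreading of the protocol.

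**What to change.** In SAP 6.5 and 6.4:

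- Delete the note on baseline detectability.
- Restrict time to CU and the change-from-baseline summaries to participants with a detectable central nasopharyngeal viral load at the SAP 6.2 baseline. The all-participant analysis may be kept as a sensitivity analysis.
- State that the CU sequence starts after baseline.
- State how a missing baseline nasopharyngeal result is handled.
- Report by arm the numbers undetectable and missing at baseline.
- Reconcile the opening sentence of SAP 6.5, which requires a post-baseline nasopharyngeal result, with the later inclusion of all ITT and Primary participants.

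The cost is SAP wording and a filter on data already collected. Baseline is pre-dose apart from the 60-minute fallback, so the restriction should not select on response to treatment. The downside is a smaller denominator for an exploratory endpoint.
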